		Screening ^a	Enrollment	Cycle 1 (21-Day Cycle)			Cycle 2 (21-Day Cycle)	Cycle 3-16 (21-Day Cycle)		EOT/ET	PTFU ^b	
	Cycle (C) Day (D) Visit Window	-28 to D1	Within 72 hours of first dose	C1 D1	C1 D2 & 4	C1 D3 & 5	C2 D1	Cx D1	Cx D16- 21	30 days (±2 days) after last dose	Minimum of 24 months	
Baseline	Informed consent	X	Randomization to Study Treatment Arm Arm 1 - brentuximab vedotin or Arm 2 - Methotrexate or Bexarotene									
	Inclusion/exclusion	X										
	Demographics	X										
	Medical history	X										
	Complete physical exam	X										
	Height	X										
	Weight ^c	X		X				X	X		X	
	Pregnancy test ^d	X		X				X	X			
Archived tissue ^e	X											
Safety Assessments	Vital signs ^f	X		X ^f				X	X		X	
	Physical exam including focused lymphoma assessment			X ^g				X	X		X	X
	ECOG performance status	X		X				X	X		X	
	Hematology/serum chemistry ^h	X						X	X		X	
	Urinalysis	X										
	12-lead ECG	X		X ⁱ								
	Immune reconstitution assessment ^l		X				X	X		X		
Disease Assessment	mSWAT and photography ^k	X	X				X	X	X	X	X	
	Circulating Sézary cells	X	X ^l					X ^l		X	X	
	FDG-PET ^m	X										
	CT ⁿ	X							X ⁿ	X ⁿ	X ⁿ	
	Quality of life assessments ^o		X				X	X		X	X	

Brentuximab vedotin (SGN-35)
Clinical Study Protocol C25001 Amendment 5, EudraCT: 2010-024215-14

	Cycle (C) Day (D) Visit Window	Screening ^a -28 to D1	Enrollment Within 72 hours of first dose	Cycle 1 (21-Day Cycle)			Cycle 2 (21-Day Cycle)	Cycle 3-16 (21-Day Cycle)		EOT/ET 30 days (±2 days) after last dose	PTFU ^b Minimum of 24 months	
				C1 D1	C1 D2 & 4	C1 D3 & 5	C2 D1	Cx D1	Cx D16- 21			
	Healthcare Utilization	X		X			X	X		X	X	
	Skin biopsy ^p (CD30 Expression)	X							X ^p	X ^p	X ^p	
	Biopsies for disease assessment ^q			X								
	Disease status/survival ^r								X	X	X	
Treatment	Brentuximab vedotin administration			X			X	X				
	Methotrexate administration ^s			X			X	X				
	Bexarotene administration ^t			Bexarotene is dosed once a day for the course of the study								
	Monitoring of concomitant medications and procedures		Recorded from screening through 30 days after the last dose of study drug.									
	Adverse event reporting ^u		Recorded from first dose of study drug through 30 days after the last dose of study drug.									
	Serious adverse events		Serious adverse events ^v will be collected from signing of the informed consent form through 30 days after the last dose of study drug									
PK/PD	PK sample ^w			X ^w	X ^w	X ^w		X ^w		X		
	CCI											

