- m FDG-PET scans will be taken at screening. No further FDG-PET scans will be required unless they are clinically indicated. FDG-PET scans taken within 8 weeks before signing the informed consent form (ICF) may be used as the screening FDG-PET scan.
- n CT scans of the neck, chest, abdomen, and pelvis will be obtained at screening. CT scans taken within 4 weeks before signing the ICF may be used for the screening CT scan if all of the following conditions are met:
- There is no nodal or visceral involvement noted
 - There is no clinically evident lymphadenopathy or splenomegaly by physical exam at the time of screening
 - The scan meets all quality criteria as outlined in the Imaging Manual
- For patients without nodal or visceral involvement (as determined by baseline CT scans), CT scans will be performed:
- During the cycle following the first skin response, ideally corresponding to the confirmation of the skin response, and 6 cycles (a minimum of 4 months) after that confirmed skin response
 - If there is a question of new or progressive disease in the LN/viscera
- For patients with baseline nodal/visceral disease, CT scans will be performed:
- At the end of Cycles 3, 6, 9, 12, and 15 (Days 16-21 or on Day 1 of the subsequent cycle), and per the follow-up schedule until disease progression
 - If there is a question of new or progressive disease in the LN/viscera
 - At EOT if the previous CT scan was performed more than 8 weeks before EOT
- o All questionnaires should be completed on Day 1 of Cycles 1, 2, 4, 6, 8, 10, 12, 14, and 16 before any other study procedures are performed, at EOT, and during posttreatment follow-up. EQ-5D, FACT-G, and Skindex-29 questionnaires will be employed for health-related quality of life (HRQoL) assessment from the patient’s perspective. Questionnaires may be collected by phone or by mail for patients not required to return to clinic for posttreatment follow-

Brentuximab vedotin (SGN-35)
Clinical Study Protocol C25001 Amendment 5, EudraCT: 2010-024215-14

		Screening ^a	Enrollment	Cycle 1 (21-Day Cycle)			Cycle 2 (21-Day Cycle)	Cycle 3-16 (21-Day Cycle)		EOT/ET	PTFU ^b
	Cycle (C) Day (D) Visit Window	-28 to D1	Within 72 hours of first dose	C1 D1	C1 D2 & 4	C1 D3 & 5	C2 D1	Cx D1	Cx D16- 21	30 days (±2 days) after last dose	Minimum of 24 months

up.

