6.9 Blinding and Unblinding

This is an open-label study; investigators and patients will know the individual treatment assignments. However, aggregate efficacy results by treatment group will be blinded to the study team, investigators, patients, and IRF, throughout the study conduct.

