7.4.13 Enrollment

A patient is considered to be enrolled in the study when randomized to a treatment arm.

Procedures for completion of the enrollment information are described in the Study Manual.

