5.4.2 Definition of Baseline Values

Unless otherwise specified, the baseline value is defined as the value collected at the time closest to, but before, the start of study drug administration.

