5.8.2 Key Secondary Efficacy Endpoints

CR rate, PFS, and changes in symptom domain per Skindex-29 assessment tool are designated as key secondary endpoints.

CR rate is defined as the proportion of patients who achieved a CR as their best response on study as determined by an IRF. A sensitivity analysis will be performed for CR per the investigator's GRS assessment. PFS is defined as the time from randomization until PD per IRF or death due to any cause, whichever occurs first. The symptom domain of Skindex-29 includes 7 items: 1) My skin hurts; 2) My skin condition burns or stings; 3) My skin itches; 4) Water bothers my skin conditions (bathing, washing hands); 5) My skin is irritated; 6) My skin is sensitive; and 7) My skin condition bleeds. The following scoring system is used for all items: never (0), rarely (1), sometimes (2), often (3), and always (4). The total score for all 7 items will be converted to a scale of 0 (no impact on quality of life) to 100 (maximum impact on quality of life) by linear transformation. The questionnaire is administered on Day 1 of Cycles 1, 2, 4, 6, 8, 10, 12, 14, and 16.

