5.8.2.1.2 Key Secondary Efficacy Analysis

Because a fixed sequential testing procedure is used between the primary endpoint and the key secondary endpoints, the key secondary endpoints will be tested only if the primary endpoint is statistically significant. The weighted Holm procedure⁽¹⁾ will be used for testing the key secondary endpoints. See Section 3.2 for details of the statistical decision rules.

Stratified log-rank test statistics will be used to compare PFS between the 2 treatment arms. The hazard ratios along with the 95% CIs will be estimated using a stratified Cox regression model. The Kaplan-Meier method will be used to estimate the distribution of the time-to-event endpoints for each treatment. Median times (if estimable), along with the 2-sided 95% CIs, will be presented.

Assuming the median PFS for the brentuximab vedotin treatment group and the physician's choice treatment group (MTX or bexarotene) are 9 and 6 months, respectively, the number of PFS events is projected to be approximately 101 at the time of the planned final analysis. This is based on an approximately 2-year enrollment period, a dropout rate of 10%, and an α level of 0.01 (2-sided), as specified in Section 3.2 per the weighted Holm procedure.

Comparison of the CR rates between the 2 treatment groups will be conducted using the stratified Cochran-Mantel-Haenszel test. The 95% CI of the difference in the response rates between the 2 treatments will also be provided. No imputation will be conducted for missing data. Patients who do not have any post baseline response assessment as specified in the protocol will be counted as nonresponders.

For skin symptoms (Skindex-29), the primary analysis will be comparing the mean symptom reduction between brentuximab vedotin and the control arms. 'Symptom reduction' is defined for each patient as the maximum reduction from baseline (sum of the 7 items related to skin symptoms normalized to a 1-100 scale). The analysis of covariance (ANCOVA) model controlling for baseline covariates (treatment group, baseline score, disease diagnosis, ECOG) will be employed for the analysis. As a sensitivity analysis, comparison of the 2 treatment groups will be conducted using the linear mixed model with repeated measures at

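### Nothing requires the first Skindex-29 to be completed before open-label randomisation, so the baseline of a key secondary endpoint may be given by patients who already know their arm

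*Protocol*

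**What the plan says.** **When the form is completed.** Protocol Schedule of Events, footnote o: "All questionnaires should be completed on Day 1 of Cycles 1, 2, 4, 6, 8, 10, 12, 14, and 16", and it continues "before any other study procedures are performed, at EOT, and during posttreatment follow-up". SAP 5.8.2 has the same start: "The questionnaire is administered on Day 1 of Cycles 1, 2, 4, 6, 8, 10, 12, 14, and 16". Neither lists a questionnaire at screening.

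**When the patient is randomised.** The Schedule of Events has an Enrollment column ahead of Cycle 1 Day 1, timed "Within 72 hours of first dose". Protocol 7.4.13 equates enrolment with randomisation: "A patient is considered to be enrolled in the study when randomized to a treatment arm". Protocol 8.1.2 places randomisation before dosing.

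**Who knows the arm.** Protocol 6.9: "investigators and patients will know the individual treatment assignments".

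**Which score is the baseline.** SAP 5.4.2: "the value collected at the time closest to, but before, the start of study drug administration". No exception is made for Skindex-29, so the Cycle 1 Day 1 score is the baseline.

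**How it is used.** SAP 5.8.2.1.2 defines the endpoint as each patient's largest fall from baseline in the symptom score, and analyses it by ANCOVA with the baseline score as a covariate. SAP 3.2 tests it with weight 0.1 in the weighted Holm family, after the primary endpoint.

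**The concern.** A covariate supports an unbiased adjusted comparison when it is fixed before allocation or cannot be affected by it. A self-reported symptom score given after the patient has learned the arm meets neither condition. Disappointment with the control arm, or optimism about the new agent, could move the answers in one arm. ANCOVA cannot remove an arm-specific shift in its own covariate.

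SAP 3.2 claims strong control of type I error for the primary and key secondary endpoints. That control presumes a valid p-value for each hypothesis. The planned supporting analyses do not test the point: the mixed model reports changes from the same baseline, and the cumulative distribution curves plot changes from it. No sensitivity analysis addresses baseline timing.

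**Working it through.** **1. The plan's own figure.** The only design figure for this endpoint is its power under weighted Holm in SAP 3.2. Inputs: success probabilities 0.85, 0.55 and 0.50 at individual two-sided 0.05; correlation 0.5; weights 0.7, 0.2 and 0.1. A simulation of 1,000,000 draws gives 40.6% for Skindex-29, 81.7% for CR, 48.2% for PFS and 83.5% for at least one. The SAP states 40%, 82%, 48% and 84%. The figures reproduce, and none depends on when the questionnaire is given.

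**2. Order of events.** The 72-hour window allows randomisation from three days before first dose to the day itself.
- Randomised on an earlier day: the form follows randomisation. Footnote o's ordering rule governs the questionnaire day and cannot reach back.
- Randomised on Cycle 1 Day 1: footnote o can be read as putting the form first, since enrolment is listed under Study Procedures (Protocol 7.4). Nothing states the order relative to the IVRS/IWRS call.

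The column alignment of the Schedule of Events is unreliable in the text available to me, so this rests on footnote o and SAP 5.8.2.

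**3. Scale.** Seven items scored 0-4 give 7 x 4 = 28 raw points mapped to 0-100. One item moved by one category is 100/28 = 3.57 points.

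**4. Illustration of bias.** The documents give no SD, slope or shift, so these are assumptions:
- SD 20-25, equal at baseline and follow-up
- slope b of follow-up on baseline 0.3-0.7
- shift d of 2-10 points in one arm
- no true effect
- 56 per arm (62 x 0.9 = 55.8)

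If the shift affects the baseline only, ANCOVA bias = b x d:
- smallest: 0.3 x 2 = 0.6 points
- middle: 0.5 x 5 = 2.5 points
- largest: 0.7 x 10 = 7.0 points

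SE = SD x sqrt(1 - b²) x sqrt(2/56). Middle case with SD 20: 20 x 0.866 x 0.189 = 3.27, so bias/SE = 0.76.

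The first Holm step for this endpoint is 0.1 x 0.05 = 0.005. The critical value is 2.807, and the false-positive rate is Φ(0.76 - 2.807) + Φ(-0.76 - 2.807) = about 0.021. A simulation of this case gave bias 2.47 and rate 0.023; with no shift it gave 0.005. Over the whole grid the rate runs from 0.0054 (SD 25, b 0.3, d 2) to 0.42 (SD 20, b 0.7, d 10). If CR and PFS have already been rejected, the test is at 0.05 and the middle case gives 0.119.

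**5. If the shift persists into follow-up.** Let the same d affect baseline and follow-up in that arm.

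| Shift | Baseline after allocation | Baseline before allocation |
|---|---|---|
| Baseline only | b x d | 0 |
| Persistent | (1 - b) x d, opposite sign | d, opposite sign |

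With b = 0.5 and d = 5, a persistent shift gives 2.5 points under the present schedule and 5 with a pre-randomisation baseline. The documents cannot say which pattern applies.

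**The case against.** The best defence has four parts.

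- **Same-day randomisation is allowed**, and footnote o then arguably puts the form first. This stands. A reader might infer that every patient gives the baseline already knowing the arm, or that no patient has a pre-randomisation score. The documents do not support that: they leave the order open.
- **Recall.** Protocol 7.4.17.5 gives Skindex-29 a 28-day recall. With randomisation at most 3 days earlier, at least 28 - 3 = 25 of the recalled days precede it. This limits how far an honest answer can move, although the answer may still be given after the arm is known.
- **Follow-up is open-label too.** Under a persistent shift, a clean baseline exposes the whole reporting difference where a contaminated one would offset part of it. This stands, and the change cannot be presented as removing open-label bias. But partial cancellation of unknown size is no reason to leave the covariate unprotected.
- **Low weight and visibility.** The endpoint has weight 0.1, is gated by ORR4, and SAP 5.10.1 summarises symptom scores by arm over time, so a baseline imbalance should show. That lowers the stakes. However, a descriptive table cannot separate chance imbalance from an effect of knowing the arm.

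**Conclusion.** The concern holds as a gap in the schedule: the first Skindex-29 is not required before randomisation, and the baseline rule is tied to first dose, not to allocation. Patients may therefore know their arm when they supply the baseline of a confirmatory test.

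A demonstrated bias would be a stronger conclusion than the documents allow. They give no SD, slope or shift, and no direction. The 0.6 to 7.0 points and the associated error rates rest wholly on the assumptions listed, including that the shift vanishes after baseline. No stated sample size or power figure changes, and the primary endpoint is untouched. This is a cheap improvement to one key secondary analysis.

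**What to change.** - **Protocol, footnote o.** Require the first Skindex-29, with FACT-G and EQ-5D, before the IVRS/IWRS randomisation call. Complete it on the day of randomisation, or within the 4 days before randomisation already used for eligibility laboratory tests.
- **Not early in screening.** Screening may start 28 days before randomisation, and the usual washout is 3 weeks. With 28-day recall, an early form could describe symptoms under previous therapy.
- **SAP 5.8.2.** State that the Skindex-29 baseline is the last score before randomisation, as an exception to 5.4.2.
- **Where baselines were already collected after randomisation.** Report how many, compare baseline scores by arm, and add a sensitivity analysis that addresses baseline timing.

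**Cost.** About one line in each document; the Protocol puts completion of the Skindex-29 at 5 to 10 minutes. The downside is a slightly older baseline: at most 3 days before first dose if completed on the day of randomisation, or 4 + 3 = 7 days at the outer edge of the laboratory window.

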Table 7-4	Response in Viscera	69
Table 7-5	Response in Blood	71
Table 7-6	Global Response Score.....	72
Table 7-7	Pharmacokinetic Sampling Time Points	74

LIST OF FIGURES

Figure 6-1	Bexarotene Risk Mitigation.....	50
Figure 7-1	mSWAT % Total Body Surface Area (TBSA) for 12 Main Body Areas	67

LIST OF ABBREVIATIONS AND GLOSSARY OF TERMS

Abbreviation	Term
ADC	antibody-drug conjugate
AE	adverse event
ALCL	anaplastic large cell lymphoma
ALK	anaplastic lymphoma kinase
ALP	alkaline phosphatase
ALT	alanine aminotransferase
ANC	absolute neutrophil count
ASCO	American Society of Clinical Oncology
AST	aspartate aminotransferase
ATA	antitherapeutic antibodies
BSA	body surface area
BUN	blood urea nitrogen
pcALCL	primary cutaneous anaplastic large cell lymphoma
CBC	complete blood count
CD30+	CD30-positive
C _{max}	maximum plasma concentration
CNS	central nervous system
CO ₂	carbon dioxide
CR	complete response
CT	computed tomography
CTCL	cutaneous T-cell lymphoma
CTACK	cutaneous T cell-attracting chemokine
DME	drug metabolizing enzymes
DNA	deoxyribonucleic acid
ECG	electrocardiogram
ECOG	Eastern Cooperative Oncology Group
eCRF	electronic case report form
EDC	electronic data capture
EFS	event-free survival
ELISA	enzyme-linked immunosorbent assay
EORTC	European Organisation for Research and Treatment of Cancer
EOS	End of Study (visit)

Brentuximab vedotin (SGN-35)
Clinical Study Protocol C25001 Amendment 5, EudraCT: 2010-024215-14

Abbreviation	Term
EOT	End of Treatment (visit)
EU	European Union
EVA	ethyl vinyl acetate
FDA	United States Food and Drug Administration
FDG	Fludeoxyglucose
GCP	Good Clinical Practice
G-CSF	granulocyte colony stimulating factor
GGT	Gamma-glutamyl transpeptidase
GI	Gastrointestinal
GLP	Good Laboratory Practices
GM-CSF	granulocyte macrophage-colony stimulating factor
GMP	Good Manufacturing Practice
GRS	global response score
Hb	Hemoglobin
Hct	Hematocrit
HDAC	histone deacetylase
HDACi	histone deacetylase inhibitor
HDL	high-density lipoprotein
HED	human equivalent dose
hERG	human ether-à-go-go related gene
HIV	human immunodeficiency virus
HL	Hodgkin lymphoma
HRQoLHU	health-related quality of lifehealthcare utilization
HU	healthcare utilization
IB	Investigator's Brochure
IC ₅₀	concentration producing 50% inhibition
ICF	informed consent form
ICH	International Conference on Harmonisation
IDMC	Independent Data Monitoring Committee
IEC	Independent Ethics Committee
IRB	Institutional Review Board
IRF	independent review facility
ISCL	International Society for Cutaneous Lymphoma
ITT	intent-to-treat

Brentuximab vedotin (SGN-35)
Clinical Study Protocol C25001 Amendment 5, EudraCT: 2010-024215-14

Abbreviation	Term
IV	intravenous; intravenously
IVRS	interactive voice response system
IWRS	interactive web response system
JCV	John Cunningham virus
LDH	lactic dehydrogenase
LDL	low density lipoprotein
LyP	lymphomatoid papulosis
MF	mycosis fungoides
MMAE	monomethylauristatin E
MedDRA	Medical Dictionary for Regulatory Activities
Millennium	Millennium Pharmaceuticals, Inc., and its affiliates
MRI	magnetic resonance imaging
mSWAT	modified severity weighted assessment tool
MTD	maximum tolerated dose
MTX	methotrexate
NCI	National Cancer Institute
NCI CTCAE	National Cancer Institute Common Terminology Criteria for Adverse Events
NOAEL	no observed adverse effect level
NYHA	New York Heart Association
ORR	objective response rate
ORR4	objective response rate lasting at least 4 months
pcALCL	primary cutaneous anaplastic large cell lymphoma
PD	progressive disease (disease progression)
PE	polyethylene
PET	positron emission tomography
PFS	progression-free survival
PK	pharmacokinetic(s)
PML	progressive multifocal leukoencephalopathy
PO	per os ; by mouth (orally)
PP	per protocol
PR	partial response
PRO	patient-reported outcome
PUVA	psoralen with ultraviolet light A
PVC	polyvinyl chloride

Brentuximab vedotin (SGN-35)**Clinical Study Protocol C25001 Amendment 5, EudraCT: 2010-024215-14**

Abbreviation	Term
RBC	red blood cell
RR	response rate
SAE	serious adverse event
sALCL	systemic anaplastic large cell lymphoma
CCI	
SD	stable disease
SDT	skin-directed therapy
SmPC	Summary of Product Characteristics
SS	Sézary Syndrome
SWAT	severity weighted assessment tool
TARC	thymus and activation regulated chemokine
TEAE	treatment-emergent adverse event
tMF	transformation mycosis fungoides
TNMB	Tumor-Node-Metastasis-Blood
TNM	Tumor-Node-Metastasis
TSEBT	total skin electron beam therapy
ULN	upper limit of the normal range
US	United States
UVA	ultraviolet light A
UVB	ultraviolet light B
WBC	white blood cell
WHO	World Health Organization

1. BACKGROUND AND STUDY RATIONALE

1.1 Scientific Background

1.1.1 Disease Under Treatment: Cutaneous T-cell Lymphoma

Cutaneous T-cell lymphoma (CTCL) is the most common cutaneous lymphoma, accounting for 72% of cases. From 1973 to 2002, reported CTCL incidence rates in the United States (US) have steadily increased. The incidence rate of CTCL from 1998 through 2002 was 9.6 per million person-years, up from 2.8 per million person-years in 1973 through 1977. CTCL incidence increases with age; it is quite low in those under 20 years (0.3 per million person-years) and it peaks in the 70- to 79-year age group (24.6 per million person-years). Cutaneous T-cell lymphoma also has notable racial and ethnic incidence differences, with much higher rates among blacks than among whites.^(1,2,3)

CTCL is characterized by clonal expansions of mature, post-thymic T cells that infiltrate the skin. The current World Health Organization (WHO) classification includes 7 major subtypes: mycosis fungoides (MF), Sézary syndrome (SS), primary cutaneous CD30-positive (CD30+) lymphoproliferative disorders (comprising primary cutaneous anaplastic large cell lymphoma [pcALCL] and Lymphomatoid papulosis [LyP]), subcutaneous panniculitis-like T-cell lymphoma, primary cutaneous $\gamma\delta$ T-cell lymphoma, primary cutaneous aggressive epidermotropic CD8+cytotoxic T-cell lymphoma, and primary cutaneous small/medium CD4+ T-cell lymphoma.

Brentuximab vedotin is an anti-CD30 targeted antibody-drug conjugate (ADC). Two major CD30-expressing CTCL subtypes have been selected for this study: MF and pcALCL.⁽⁴⁾

1.1.1.1 Mycosis Fungoides

Mycosis fungoides, the most common form of CTCL, accounts for approximately 44% of all cutaneous lymphomas. An indolent disease with a protracted course, it occurs most often in middle-aged to elderly adults, with a male (66%) predominance. The 10-year disease-specific survival for patients who have progressed to the tumor stage is approximately 42%; this drops to 20% with histologically proven lymph-node involvement.⁽⁵⁾ The skin lesions of MF tend to be on the trunk and include erythematous patches, thickened plaques, nodular tumors, and generalized erythroderma. Patches and plaques may persist for years and eventually spread and progress to tumors; dissemination to lymph nodes and visceral organs is a late manifestation.

Brentuximab vedotin (SGN-35)

Clinical Study Protocol C25001 Amendment 5, EudraCT: 2010-024215-14

Although the clinical course of MF is usually indolent, occasionally, individuals with MF develop a morphologic transformation (tMF) from small- to intermediate-sized cerebriform cells to a large cell variant. Large cells in excess of 25% of the total lymphoid infiltrate typically characterize large-cell transformation and incidence of such transformation reportedly ranges between 8% and 55%.^(6, 7) Approximately 30% to 50% of tMF cases express CD30 by large cells, with a positivity of more than 75% in approximately 15% of tMF cases.⁽⁵⁾ Edinger et al showed that in 47 nontransformed MF biopsies, at least rare dermal CD30-positive cells were present in all cases. More than 25% CD30-positive lymphoid cells were present in the epidermis and dermis in 12 (25%) and 2 (4%) cases, respectively, indicating that CD30 staining can be prominent in MF without transformation.⁽⁸⁾

